#### 4.7.1.4 Multiple Comparisons/Multiplicity

Analysis of one primary variable [Change in Hb] and one time point of primary interest [Week 6 visit] has been defined for this study. Though 3 pairwise comparison between placebo and dosed group is planned, step-down procedure will be used to control the overall type I error rate. The secondary variables defined are intended to provide supportive evidence relating to the primary objective and no labeling claims are intended. Though one preliminary analysis is planned before the final analysis, primary analysis will not be changed. Hence no adjustments for multiplicity are required.

#### 4.7.1.5 Preliminary (6-Week) Analysis

After all subject performed assessment of the Week 6 Visit, preliminary analysis will be performed. As the study conduct and final analysis will not be modified by this analysis, no alpha adjustment is proposed. It is expected that this 6-week data will be identical for the preliminary analysis and the final analysis of the complete dataset. Any changes between the preliminary analysis and the final analysis will be documented. The preliminary analysis will be performed by the independent unblinded team. All data through the cutoff date of the last subject randomized who completes week 6 will be analyzed. Blinding of blinded team and investigators will be maintained to prevent potential bias.

#### 4.7.1.6 Examination of Subgroups

Not Applicable. No subgroup analysis is planned.

### **4.7.2 Primary Efficacy Variable – Mean Change in Hb from Pre-treatment to the End of the Primary Efficacy Period (Week 6)**

The primary variable for the assessment of efficacy is the change from pre-treatment to Week 6 in Hb (g/dL). Change in Hb is defined as the Hb measured at the Week 6 visit minus the mean pre-treatment Hb. Pre-treatment Hb is defined as the average of 2 Hb values obtained prior to treatment based on the qualifying screening Hb value and the Hb value at the baseline visit.

For the primary analysis, the LOCF approach will be used to impute missing data. Complete-case analysis will be performed for sensitivity at the scheduled Week 6 visit.

#### 4.7.2.1 Summary of actual value and change in Hb at week 6

The primary analysis population for efficacy will be MITT and PP population. The following summary will be provided:

- A summary of actual value of Hb by treatment group at baseline and week 6. A summary of the change (absolute and percent) from baseline in Hb by treatment group at week 6. 1st and 3rd quartiles (Q1, Q3) as well as the mean, SD, median, minimum, maximum and number of observations will be shown. P values for overall

comparison and treated groups vs. placebo on change from baseline will also be presented.

- A waterfall plot for absolute Hb change from baseline for each treatment group at week 6.

The effect of treatment in terms of the change from pre-treatment to Week 6 in Hb will be analyzed using a one-way analysis of covariance (ANCOVA). The statistical model will assess the main effect of treatment, adjusted for pre-treatment average. Least-squares (LS) means for each treatment and their 95% confidence intervals (CIs) will be presented. Three post-hoc pairwise comparison, i.e., Placebo vs 150 mg, placebo vs 300 mg, and placebo vs 600 mg, will be done. Unadjusted one-way analysis of variance (ANOVA) will be performed for sensitivity.

The simple linear regression between the change from pre-treatment to Week 6 in Hb and dose will be calculated. The regression coefficients and their standard errors, p-values of test of regression parameters and their 95% CIs will be presented. The test of slope parameter will be used to evaluate dose response relationship.

As sensitivity analyses, efficacy endpoints will also be analyzed using the PP population.

A by-subject listing of actual values and change (absolute and percent) from baseline in Hb will be provided.

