## 2 STUDY OBJECTIVES

### 2.1 Primary Objective and Endpoint

The primary objective of this study is to assess the dose-response relationship between oral vadadustat once daily dosing for 6 weeks and the change in Hb in Japanese subjects with anemia secondary to NDD-CKD; this is to define the starting dose for use in Phase 3 clinical studies in Japan.

The primary endpoint that will be used to assess this objective is the mean change in Hb levels from pre-treatment to the end of the primary efficacy period (Week 6). Pre-treatment Hb is defined as the average of 2 Hb values obtained prior to treatment based on the qualifying screening Hb value and the Hb value at the baseline visit.

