#### 4.7 Efficacy Evaluation

##### 4.7.1 Analysis and Data Conventions

This study is designed to test for dose-response relationship. An analysis of covariance (ANCOVA) model will be used to compare absolute change from pre-treatment in Hb between the three vadadustat dosing groups and the placebo group. The model will include treatment assignment (3 dosed groups and one placebo group) and pre-treatment Hb value as a covariate. A step-down procedure will be used to control the overall type I error rate for the multiple comparisons. Testing of the highest dose compared with

placebo will be conducted first. If and only if this comparison is significant, then testing will proceed to comparison of the next lower dose and placebo, and so on. Therefore, no multiplicity adjustment will be needed for this analysis.

A linear regression dose-response modeling will be performed as a secondary analysis.

$$Y = \beta_0 + \beta_{dose}X$$

where Y is change in Hb and X is vadadustat dose.  $\beta_x$ s are parameters of the model.  $\beta_0$  is intercept and  $\beta_{dose}$  is slope, respectively.

The null hypothesis for the dose response will be that the regression coefficient of slope parameter is zero. The alternative hypothesis will be that the regression coefficient is not zero. Symbolically, this is expressed as follows:

$$H_0: \beta_{dose} = 0$$
$$H_1: \beta_{dose} \neq 0$$

This hypothesis will be tested using a 0.05 two-sided significance level.

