#### 4.7.1.2 Adjustments for Covariates

The primary efficacy analysis will be adjusted for the pre-treatment measure of primary efficacy variable.

An ‘unadjusted’ sensitivity analysis will be performed to assess the robustness of the study conclusion.

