#### 4.10 Determination of Sample Size

The target enrollment will be approximately 48 subjects for the study with 12 subjects enrolled in each of the 4 treatment groups.

The study is powered based on a comparison of the highest dose vadadustat group (600 mg daily) and the placebo group. Based on the results from Study AKB-6548-CI-0005 that was conducted in the United States and evaluated vadadustat in patients with anemia secondary to NDD-CKD, it is assumed that the expected mean Hb changes from

baseline to Week 6 will be approximately 0 mg/dL for the placebo group and 1.35 g/dL for the highest dose vadadustat group (600 mg daily), with a common standard deviation of 0.68 g/dL across treatment groups. With these assumptions, the study with n=12 subjects per group will have >95% power to detect the difference between treatment group and control group, at 2-sided alpha of 0.05.

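### The secondary dose-response regression uses dose alone; adding the pre-treatment Hb average, already the ANCOVA covariate, would tighten the slope estimate at almost no cost (minor)

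*SAP*

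**What the plan says.** SAP section 2.1 sets the aim: "The primary objective of this study is to assess the dose-response relationship between oral vadadustat once daily dosing for 6 weeks". The response is Hb change, and the purpose is to define a Phase 3 starting dose. Two analyses of the Week 6 change in Hb bear on it.

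- **ANCOVA with step-down comparisons of each dose against placebo** (sections 4.7.1 and 4.7.2.1). "The model will include treatment assignment (3 dosed groups and one placebo group) and pre-treatment Hb value as a covariate". Section 4.7.1.2 gives the general rule: "The primary efficacy analysis will be adjusted for the pre-treatment measure of primary efficacy variable". An unadjusted ANOVA is the sensitivity analysis.
- **Linear regression on dose.** Section 4.7.1 gives its rank: "A linear regression dose-response modeling will be performed as a secondary analysis". The model there is Y = β0 + β_dose·X, where Y is the change in Hb and X the vadadustat dose. On the slope: "This hypothesis will be tested using a 0.05 two-sided significance level". Section 4.7.2.1 repeats the model, "The simple linear regression between the change from pre-treatment to Week 6 in Hb and dose will be calculated", and assigns its role: "The test of slope parameter will be used to evaluate dose response relationship".

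No version of the regression includes pre-treatment Hb.

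**The concern.** The SAP's other Week 6 models for continuous variables are ANCOVAs adjusted for the starting value, with an unadjusted ANOVA alongside: Hb in 4.7.2.1, hematocrit, RBC and reticulocyte counts in 4.7.3, CRP and VEGF in 4.8.4.8. The dose-response slope is the exception, and no reason is given.

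Y is Week 6 Hb minus the pre-treatment average, so the covariate is part of the outcome. Y would be uncorrelated with it only if, within a dose group, Week 6 Hb rose one-for-one with pre-treatment Hb. Any other relation leaves explainable variance in the residual. With 12 subjects per group, a chance difference in pre-treatment Hb also passes into the unadjusted slope but not into the adjusted least-squares means reported in the same section. At stake are the width of the slope's interval and its agreement with those means.

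**Working it through.** **Inputs from the SAP.** 12 subjects in each of 4 groups, SD of change 0.68 g/dL, mean change 0 on placebo and 1.35 g/dL at 600 mg, and power above 95% "at 2-sided alpha of 0.05" (section 4.10). Doses are 0, 150, 300 and 600 mg (section 3.1).

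**Assumptions, not in the SAP.** The within-dose correlation r between pre-treatment Hb and change; a mean response linear in dose; all 48 subjects contributing.

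**1. The plan's own figure.** Standard error of the 600 mg minus placebo difference = 0.68 × √(2/12) = 0.278, and 1.35/0.278 = 4.86. Power is 99.8% by the normal approximation and 99.6% by the noncentral t with 22 df. The stated >95% reproduces.

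**2. Unadjusted slope.** Mean dose = 262.5 mg. Squared deviations are 68,906.25, 12,656.25, 1,406.25 and 113,906.25, which sum to 196,875. Sxx = 12 × 196,875 = 2,362,500.

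- SE per 600 mg = 600 × 0.68/√2,362,500 = 0.265 g/dL (0.0442 per 100 mg).
- 95% half-width with 46 df = 2.013 × 0.265 = 0.53 g/dL per 600 mg.
- Power for a rise of 1.35 g/dL over 600 mg = 99.87%.

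**3. Adjusted slope.** The residual SD becomes 0.68 × √(1 − r²), with 45 df. The equivalent sample size is 48/(1 − r²).

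| assumed \|r\| | SE per 100 mg | half-width per 600 mg | interval narrower by | equivalent N | power if the 600 mg effect were 0.7 g/dL (assumed) |
|---|---|---|---|---|---|
| unadjusted | 0.0442 | 0.53 | – | 48 | 73.3% |
| 0.2 | 0.0433 | 0.52 | 2.0% | 50 | 75.0% |
| 0.3 | 0.0422 | 0.51 | 4.5% | 53 | 77.2% |
| 0.5 | 0.0383 | 0.46 | 13.3% | 64 | 84.6% |
| 0.7 | 0.0316 | 0.38 | 28.5% | 94 | 95.1% |

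Under the planned 1.35 g/dL, adjusted power is at least 99.9% in every adjusted row.

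**4. Cost when the covariate is useless.** At r = 0 the lost degree of freedom widens the interval by 0.1%. Allowing for chance imbalance in the covariate, by a factor √(45/44) = 1.011, the widening is about 1.2%. With the same allowance the gains in the table become 0.9%, 3.5%, 12.4% and 27.7%, and break-even is at |r| = 0.15.

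**5. Plausibility of the range.** If pre-treatment and Week 6 Hb had equal within-dose variances and correlation ρ (a further assumption), then |r| = √((1 − ρ)/2). This gives 0.22 at ρ = 0.9, 0.39 at ρ = 0.7 and 0.50 at ρ = 0.5. A value of 0.7 would need ρ = 1 − 2 × 0.49 = 0.02, so that row is an outer bound.

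**The case against.** The strongest reply is that nothing in the plan is broken. The regression is labelled secondary. The primary step-down comparisons are adjusted, as section 4.7.1.2 requires, so the sections do not contradict each other. Under randomisation the unadjusted slope test is valid, and its standard error already allows for chance imbalance. Under the plan's own effect and SD no conclusion would change. All of this stands, and it limits the point to efficiency and consistency.

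Three stronger readings are tempting and are not supported.

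- *That the primary objective rests on an unadjusted test.* Section 4.7.2.1 does use the slope test to evaluate dose response, but the adjusted ANCOVA serves the same objective and ranks first.
- *That the slope and its interval determine the Phase 3 starting dose.* The SAP does not say so. It also reports adjusted least-squares means with 95% intervals at each dose, from which any departure from a straight line would be visible.
- *That X might be the dose actually taken, which responds to Hb because doses can be cut before Week 6.* Section 4.4.2 analyses efficacy as randomised, and section 4.7.1.3 says subjects with a dose reduction are not treated differently. Together they point to randomised dose, although the model statement does not use that term.

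The reply is also right that the size of the gain depends on a correlation the SAP does not give, so no single figure can be claimed.

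**Conclusion.** The point holds as a free improvement of minor severity. The slope model omits a covariate that is already collected, already averaged and already used for the same outcome. The gain is an interval narrower by about 2% to 13% for |r| of 0.2 to 0.5, and about 28% at the outer bound of 0.7, against about 1% wider if r is zero. These figures rest on the planning SD, 12 subjects per group and the assumed r. Power is above 99% with or without the covariate if the planned 1.35 g/dL is right and the mean is linear in dose. It matters only if the true effect is much smaller: at an assumed 0.7 g/dL it rises from 73.3% to 77.2% at |r| = 0.3 and to 84.6% at |r| = 0.5. The validity of the test is not in question.

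**What to change.** In sections 4.7.1 and 4.7.2.1, fit

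Y = β0 + β_dose × (randomised dose, placebo = 0) + β1 × (pre-treatment Hb average),

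test β_dose at two-sided 0.05, and report it with its standard error and 95% interval. Keep the simple regression as the unadjusted sensitivity analysis, matching the ANCOVA and ANOVA pair. Naming randomised dose in the formula also settles the definition of X.

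The cost is one model term, a sentence in each section and one degree of freedom. No new data are needed.

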#### 4.7.2.2 Summary of actual value and change in Hb from baseline to week 6 and beyond

The analysis population for efficacy will be MITT and PP population. The following summary will be provided:

- A summary of actual value of Hb by treatment group and study visits. 1st and 3rd quartiles (Q1, Q3) as well as the mean, SD, median, minimum, maximum and number of observations will be shown. Summary of pre-treatment average will also be presented.
- A summary of the change (absolute and percent) from baseline in Hb by treatment group and study visits.
- A plot showing the mean Hb value over time within each treatment group. 95% CI of these means will be shown as error bar and sample size in each group at each time point will be shown.
- Plots of individual profile of Hb values over time within each treatment group.
- Box plots of absolute Hb changes from baseline for each treatment group at each post-treatment study visit to week 6
- Box plots of absolute Hb changes from baseline for each treatment group at each post-treatment study visit to week 16

A by-subject listing of actual values and change (absolute and percent) from baseline in Hb will be provided.

### 4.7.3 Secondary Efficacy Variables

The analysis population for efficacy will be MITT and PP population.

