#### 4.4.2 Analysis Populations for the Efficacy Analyses

The efficacy summaries and analyses will be based on the **modified intent-to-treat (MITT) population**. The MITT population is defined as all randomized subjects who have received at least 1 dose of study medication and have a pre-treatment Hb average defined as the average of the qualifying screening value and the baseline value, and at least one post-baseline Hb measurement. In the event that a subject is allocated the incorrect study treatment as per the study randomization list, subjects will be summarized and analyzed ‘as randomized’ i.e. by randomized treatment group.

For the efficacy variables, sensitivity analyses will be performed on the **per-protocol (PP) population** to assess the robustness of the study conclusions to the choice of analysis population. The PP population is defined as the subjects in the MITT population who have completed the study and have efficacy data through Week 6, have a study medication compliance of  $\geq 80\%$ , and do not have any major protocol deviations expected to significantly affect the primary efficacy endpoint. Subjects with major protocol deviations expected to significantly affect the primary efficacy endpoint will be identified and documented prior to data unblinding.

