#### Rescue therapy & ESA administration

Initiation of rescue therapy will be analyzed.

The following Rescue therapy summaries will be provided:

- A summary of the number and percentage of subjects requiring rescue with RBC transfusion from baseline to the end of the primary efficacy period (Week 6) and the end of the dose adjustment and maintenance period (Week 16)
- A summary of the number and percentage of subjects requiring rescue with ESAs from baseline to the end of the primary efficacy period (Week 6) and the end of the dose adjustment and maintenance period (Week 16). An ESA rescue is defined to fulfill the following 4 criteria simultaneously:

1. ESA administration, and
2. ESA administered because the subject experienced a clinically significant worsening of their anemia or symptoms of anemia, and
3. ESA administered because the subject's Hb level is <9.0 g/dL, and
4. **Subjects' reason for early study withdrawal is because of "Worsening of anemia requiring ESA rescue or blood transfusion".**

The following ESA administration summaries will be provided:

- A summary of the number and percentage of subjects requiring administration with ESAs from baseline to the end of the primary efficacy period (Week 6) and the end of the dose adjustment and maintenance period (Week 16)

The effect of treatment in terms of the proportion of subjects requiring with RBC transfusion / ESAs administration will be analyzed using Fisher's exact test. Three post-hoc pairwise comparison, i.e., Placebo vs 150 mg, placebo vs 300 mg, and placebo vs 600 mg, will be done.

By-subject listings of rescue therapies and ESA administration will be provided by treatment group.

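### ESA rescue is also to be analysed in the per-protocol set, but its definition requires early withdrawal while per-protocol membership requires completion, so the per-protocol rate is zero or nearly so by construction

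*SAP*

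**What the plan says.** Three statements in the current SAP (the version carrying Amendment 3) meet here.

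- **Population.** Section 4.7.3 opens with one unqualified sentence: "The analysis population for efficacy will be MITT and PP population". The rescue subsection belongs to 4.7.3 and names no other population.
- **PP membership.** Section 4.4.2 takes the "subjects in the MITT population who have completed the study and have efficacy data through Week 6", and adds conditions on compliance and major deviations. The stated purpose of PP is to test whether conclusions are robust to the choice of population.
- **ESA rescue.** Under Rescue therapy & ESA administration, "An ESA rescue is defined to fulfill the following 4 criteria simultaneously". The fourth criterion is that the subject's "reason for early study withdrawal is because of" worsening anemia needing ESA rescue or transfusion.

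The same subsection has two outputs without a withdrawal criterion: RBC-transfusion rescue, and a separate summary of ESA administration. The Fisher test is assigned to these, since it is the "proportion of subjects requiring with RBC transfusion / ESAs administration will be analyzed using" Fisher's exact test.

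For percentages in general, section 4.2 uses as denominator the subjects who have data at the time point concerned.

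**The concern.** Withdrawal is part of what makes a subject an ESA rescue, and completion is part of what makes a subject PP. The analysis set is therefore chosen on the outcome that it is meant to analyse. A PP table of ESA rescue that shows no events in any arm would say nothing about the drug, yet it would stand beside the MITT table as a sensitivity analysis.

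The collision arises from the fourth criterion, which Amendment 3 added (section 5.1.1.3, Change#4). Rescue in the first six weeks matters most, because that is the only placebo-controlled window: section 3.1 switches placebo subjects to vadadustat after Week 6.

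**Working it through.** **The plan's own figure.** The SAP states no expected rescue rate. Its only design figure is power above 95% with 12 per group (section 4.10). That reproduces: the noncentrality is 1.35 / (0.68 × √(2/12)) = 4.86, and the noncentral t on 22 df gives 99.6%. The point below uses only the 12 per group.

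**Step 1: set logic.** An ESA-rescued subject has withdrawn early (criterion 4). The completion phrase in 4.4.2 can be read in two ways.

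- *Whole-study completion.* No ESA-rescued subject can be in PP. The rate is 0/n in every arm at both time points.
- *Completion through Week 6.* A subject rescued and withdrawn before Week 6 is not in PP. A subject who withdrew after Week 6 can be. The only ESA rescue that can count in PP within the first six weeks is one where the ESA was given before Week 6 and withdrawal came after that visit.

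**Step 2: size.** The SAP gives no counts, so these are assumed. Placebo has 2 subjects rescued and withdrawn before Week 6 and 1 after. The active arm has 0/12. Everyone else qualifies for PP.

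| Placebo ESA rescue | By Week 6 | By Week 16 |
|---|---|---|
| MITT, all 12 as denominator | 2/12 = 16.7% | 3/12 = 25.0% |
| PP, whole study (12 − 3 = 9) | 0/9 | 0/9 |
| PP, through Week 6 (12 − 2 = 10) | 0/10 | 1/10 = 10.0% |

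The one event left in the last row falls after the placebo subjects have been switched to vadadustat.

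**Step 3: effect on the tested variable.** Criterion 1 of ESA rescue is ESA administration, so every ESA-rescued subject is also an ESA-administration case. On the whole-study reading, PP drops all of them from the Fisher test. As an extreme assumed case, suppose that all ESA administrations on placebo meet the four criteria and that there are none on 600 mg.

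- 5/12 vs 0/12 in MITT: two-sided p = 2 × C(12,5)/C(24,5) = 2 × 792/42504 = 0.037. In PP it becomes 0/7 vs 0/12, p = 1.00.
- 3/12 vs 0/12 in MITT: p = 2 × C(12,3)/C(24,3) = 2 × 220/2024 = 0.217. In PP it becomes 0/9 vs 0/12, p = 1.00.

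If only 3 of 5 ESA-treated placebo subjects meet the four criteria, PP can keep the other 2. The rate is then 2/9 = 22.2% instead of 5/12 = 41.7%. The test is depleted but not empty.

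**Step 4: denominator.** Under section 4.2, the three withdrawn subjects in Step 2 have no Week 16 data. The denominator would fall to 9, giving 3/9 = 33.3% if the events are still counted and 0/9 if they are not. MITT alone does not settle the rate unless the denominator is stated.

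**The case against.** The strongest reply is that the SAP favours the Week 6 reading of completion. Disposition (4.3.1) reports completion through the Week 6 visit. PP serves the Week 6 primary endpoint. The preliminary analysis (4.7.1.5) is run once all subjects have had that visit, when a whole-study PP set could not yet be formed. This is a fair argument, and on that reading the Week 16 rate can exceed zero. It does not restore the rescues with withdrawal before Week 6, and the wording of 4.4.2 still allows both readings.

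The impact is also limited. PP is a sensitivity set, MITT results are reported alongside it, and section 4.7.1.4 treats the secondary variables as supportive with no labeling claims. That stands, and the primary analysis is untouched.

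A reader might infer more than the text supports:

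- *That every rescue is zero in PP.* The four criteria attach to ESA rescue only. RBC-transfusion rescue has no withdrawal condition. The withdrawal reason mentions transfusion, but the SAP does not require transfused subjects to withdraw.
- *That the three Fisher tests must give p = 1.00.* The current text tests RBC transfusion / ESA administration, not four-criterion ESA rescue. The p = 1.00 results in Step 3 need the added assumption stated there.
- *That PP removes treatment failures generally.* It does not exclude for lack of Hb response. A completer who never reaches the target range stays in PP and is censored.
- *That PP should be dropped for all Week 16 and time-to-target outputs.* That would be a preference, and it would put 4.7.3 out of line with 4.7.2.2, which keeps PP for Hb over the whole study.

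**Conclusion.** Wrong as written, for ESA rescue in PP. If PP requires completion of the whole study, the rate is 0% in every arm at both time points by definition. If it requires completion through Week 6, every rescue with withdrawal before Week 6 is lost, and the placebo-controlled rate is zero or nearly so by construction, while later rescues can remain. On the whole-study reading, the ESA-administration summary and its tests also lose every ESA-rescued subject, without being forced to zero.

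The logical result rests only on the SAP text. Its size depends on how many ESA rescues occur, which the SAP does not state; the 25.0% against 0% or 10.0% and the Fisher p-values are illustrations on assumed counts. The defect is confined to a secondary sensitivity output.

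**What to change.** 1. In section 4.7.3, under Rescue therapy & ESA administration, add: 'All rescue and ESA-administration summaries and tests are performed in the MITT population only. The denominator is all MITT subjects in the treatment group, whether or not they provide data at the time point.' This overrides the general denominator rule in section 4.2 for these outputs.
2. In section 4.4.2, state whether PP requires completion through Week 6 or of the whole study.

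PP may stay for the other secondary variables, and the ESA-rescue definition itself need not change. With the assumed counts above, the reported placebo rates would be 2/12 by Week 6 and 3/12 by Week 16.

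The cost is a few sentences in the SAP and fewer tables. No new data are needed.
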